Because local gastrointestinal intolerance is the primary adverse effect, safety margins based on mg/kg/day of ENT-01 are considered an appropriate safety metric based on allometric comparisons of gastrointestinal dimensions between species (Kararli, 1995; Sharma and McNeill, 2009).

The proposed starting dose in the Stage 1 segment of the planned trial is 25 mg (0.33 mg/kg for a 75 kg subject). The NOAEL of a single oral dose in the rat is \geq 1000 mg/kg, and in the dog, \geq 200 mg/kg representing a relative safety margin for the proposed starting dose of about 3000x based on the rat and about 600x based on the dog. The proposed maximum single dose in Stage 1 is 200 mg (2.7 mg/kg for a 75 kg subject) is covered by a safety margin of about 300x based on the rat, and about 70x based on the dog.

The maximum proposed dose to be evaluated in Stage 2 of the planned trial is 175 mg/kg/day (2.3 mg/kg/day for a 75 kg subject), and the total daily dosing exposure will last no longer than 25 days. The NOAEL of 25 daily dosing in the rat is \geq 80 mg/kg/day and in the dog, \geq 20 mg/kg/day, representing a relative safety margin for the proposed maximum daily dose of at least 35x based on the rat, and at least 9x based on the dog.

No gastrointestinal lesions, either macroscopic or microscopic, were associated with oral dosing of ENT-01 any of the non-clinical studies conducted. Systemic blood levels of ENT-01 will be determined in this clinical trial. The chemical structure of squalamine (highly water soluble, amphipathic cationic zwitterion of molecular weight 628) predicts poor oral bioavailability. Squalamine is well tolerated when administered by continuous intravenous dosing at 200-300 mg/m² over days to months of 5 day continuous infusions. At these dosing rates steady state plasma concentrations range between 5-10 µg/ml. Reversible elevation of hepatic enzymes is the major dose limiting toxicity, observed at dose rates above 300 mg/ m², which is understood since squalamine is cleared by the liver.

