Participants will receive a phone call and be asked about adverse events. They will also provide their daily stool chart to assess the severity of the constipation and use of laxatives, softeners, bulking agents and suppositories. *Patients with two or fewer complete, spontaneous bowel movements will qualify for the treatment period. A bowel movement occurring within 24 hours of suppository, softener, bulking agent or enema use will NOT be counted. A spontaneous stool is a stool occurring in the absence of a laxative, softener, bulking agent or suppository.* PAC-SYM and PAC-QOL to be administrated on day 14, or at the clinic at Dose 1 visit the following day if they fail to bring the completed survey.

PERIOD 2.1 (Stage 1): Single dose

Safety, tolerability and pharmacokinetics of orally administered single-dose ENT-01 in Sentinel Group

Duration: 22-57 days

The 10 patients in the sentinel group will be assigned to Cohort 1 and will participate in 8 single dosing periods.

Subjects	D1	D4-8	D7-15	D10-22	D13-29	D16-36	D19-43	D22-50	D25-57
1-2	25mg	50mg	75mg	100mg	125mg	150mg	175mg	200mg	
3-4		25mg	50mg	75mg	100mg	125mg	150mg	175mg	200mg
5-6		25mg	50mg	75mg	100mg	125mg	150mg	175mg	200mg
7-8		25mg	50mg	75mg	100mg	125mg	150mg	175mg	200mg
9-10		25mg	50mg	75mg	100mg	125mg	150mg	175mg	200mg

All 10 patients will be pre-selected in advance of check-in for their first scheduled dosing period. All laxatives, suppositories, softeners, bulking agents and enemas will be disallowed during the 24-hour period before or after the administration of study medication. Patients will wear the I-Button continuously for the entire dosing period. The first two patients (subjects 1-2) will first be admitted and given a single dose. The study will be conducted at a hospital-based clinical unit and patients will be monitored for 24 hours after the dose. Unless there are any safety

concerns, patients will be released at this time and brought back for the next dosing on Day 4-8 (D4-8), after a minimum of a 72 hour observation period. Dopamine will be taken prior to the clinic visit on an empty stomach. Patients will self-administer the study medication during their clinic visit. The dose will be taken on an empty stomach along with 8 oz. of water after baseline observations in the clinic. The patient will not be allowed to ingest any food for at least 60 minutes after study medication.

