Each dose period will be staggered, so that patients 1-2 will be administered a single dose of the drug at the lowest dose of 25mg. Once 24 hours have elapsed, and provided there are no safety concerns, they will be sent home and brought back on day 4-8 for the next dose. During the days the patients are home, they will complete the daily diaries and e-mail them to the study coordinators. The study coordinators will call the patients every other day starting on the day following discharge for each dose and determine with the patient if a suppository or laxative is needed, as well as inquiring about any adverse events. Diary information will also be discussed with the patients during the telephone calls. Patients 3-10 will be dosed after the first two patients have been observed for 72 hours, i.e. on Day 4. Patients 1-2 will also be brought back on Day 4-8 and will be given a single dose of 50mg. Once another 24 hours have elapsed and provided there are no safety concerns, they will all be sent home and instructed to return on Day 7 for the next dosing level. This single dosing regimen will be continued until each patient has been given a single dose of 200mg or has reached a dose limiting toxicity (DLT). DLT will be the dose which induces repeated vomiting, diarrhea, abdominal pain or symptomatic postural hypotension within 24 hours of dosing. Maximum tolerated dose (MTD) will be the highest dose for which there was no more than 1 DLT endpoint (refer to Section 9.8, DLT endpoint criteria). A review of safety, tolerability and adverse events will occur prior to administration of each dose level and at the end of Period 2 with DSMB. After the last dose of medication, BDI, MMSE, Trail-making A and B, NMSQ, UM-PDHQ, PFS-16, RBDQ, PDSS, PAC-SYM and PAC-QOL will be administered.

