MTD: Maximum Tolerated Dose **ID: Intolerant Dose** No prokinetic response MTD ID Day10 Day13 Subject Day 1 Day4 Day7 Day16 Day19 Day22 Day 25 25mg 50mg 100mg 75mg >125mg 150mg 175mg 2 25mg 50mg 75mg 100mg 125mg 150mg 175mg 200mg Stage 1 Period 2.1 3 50mg 75mg 100mg 125mg 150mg 175mg 25mg (COHORT 1) 4 25mg 50mg 75mg 100mg 125mg 150mg Single dose 125mg 5 25mg 50mg 100mg 150mg 75mg 175mg 200mg safety, 50mg 100mg 125mg 6 75mg 25mg tolerability and 50mg 100mg 7 25mg 75mg 125mg 150mg 175mg identification of 8 25mg 50mg 75mg 100mg 125mg 150mg prokinetic dose 50mg 100mg 125mg 150mg 25mg 75mg → 175mg 200mg 10 25mg 50mg 75mg 100mg 125mg 150mg 175mg 200mg STDE DOSE in this example is 75 mg, that being the lowest dose that is safe and tolerable in all subjects and has a prokinetic effect in at least some

Schematic for Stage 1, Period 2.1: Hypothetical dosing regimens

Pharmacokinetics: Timed blood samples (5.0 mL) will be collected into Li-Heparin treated tubes for analysis of ENT-01 plasma concentrations. Plasma samples will be obtained for pharmacokinetics before dose administration and at 1, 2, 4, 8, and 24 hours.

Once collected, PK samples will be stored in a -20°C or -70°C freezer until time of shipment. Labels and appropriate shipping materials will be provided to sites. The concentration of study drug will be determined from the plasma samples using a validated analytical method. Details of the method validation and sample analysis will be included with the final clinical study report.

Individual stopping criteria:

The complete panel of Blood Chemistries described in Appendix 1 are to be drawn 24 hours after each dose. Results will be reviewed the evening before the following dose. In addition, any patient with at least 1 DLT endpoint (see **Section 9.8**), or with another non-DLT gastrointestinal AE > grade 3 that is at least possibly attributable to ENT-01, or elevated AST, ALT, or total bilirubin > 3x ULN or a reduction of body weight of 10% or more from baseline will be terminated. ENT-01 has very little systemic absorption, and hence adverse events are expected to be within the gastrointestinal system.

Refer to Section 9.12 for Adverse Event Grading and to Section 9.8 for DLT Endpoint

Criteria.

Go/No-go decision:

Safety: We are assuming that no more than 1 patient out of ten (10%) will have an adverse event

of grade 4 or 5 that is at least possibly related to ENT-01 in dose levels thought to be below

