therapeutic effect. Should there be more than 1 patient with AE grade 4 or 5 that is at least possibly

related to ENT-01 for doses less than 200 mg, the study will be put on an immediate safety hold

until an emergency DSMB meeting can be held to evaluate the study for possible discontinuation.

Dose-finding: Beyond the safety and tolerability, this Period will allow us to determine the dose

which is safe and tolerable in all 10 patients (STD) and which has a pro-kinetic effect in at least

some patients (STDE: Safe and Tolerable dose in all and pro-kinetic Effect in at least some). We

will start Period 3 with the STDE.

PERIOD 2.2 (Stage 1): Washout

Duration: 2 weeks

Patients will be observed off study drug and adverse events will be recorded. They will

continue to keep a daily diary throughout the period. They will continue to wear the I-Button for

five 24 hour periods between Days 1 and 5. During the second week, they will be restarted on all

original medications but will continue their diaries until the termination of the study. They will be

seen prior to study termination and BDI, MMSE, Trail making A and B, NMSQ, UM-PDHQ, PFS-

16, RBDQ, PDSS, PAQ-SYM and PAC-QOL will be administered.

Visit 2: Day 14

Patients will be reviewed prior to discharge and any adverse events noted.

DSMB review of Stage 1: The DSMB will determine whether to proceed to Stage 2.

PERIOD 3.1 (Stage 2a)

Run-in period for Cohort 2 (n=40)

Duration: 2 weeks

Conducted at home.

28

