
be calculated as CSBM/#fixed dose days x 7. The primary end-point is obtained by comparing this number to the baseline CSBM obtained at the end of the run-in period.

2: SUPPOSITORY/ENEMA RESCUE USE DURING DOSE ESCALATION IN STAGE

Patients will wear I-Buttons starting with the lowest dose (e.g. 75 mg) and will remove them on day 5 of the wash-out period. The remaining 30 patients will start on STDE (e.g. 75mg) as soon as they have completed the Run-in Period and will follow the same incremental dosing regimen until they reach their LSTDEi or maximum tolerated dose. These regimens and adjustments are shown in the schematic below.

Once the LSTDEi has been established, each patient will remain on that dose for two to four additional days prior to randomization in Period 4 (5 to 7 consecutive days on prokinetic dose)

N.B. Primary end-point is obtained by comparing stool diary at this point with baseline diary on rescue medication at the end of the run-in period.

Visit 3 for non-PK patients (Day before Randomization).

Non- PK patients will come to the site for a visit to return any unused study drug (B), receive 6 daily doses of randomized drug (A or C), Sitzmarks capsules and will complete all the questionnaires listed below. They will be sent home with 6 daily doses of A or C and Sitzmarks capsules and will return for Visit 4 on Day 6 of randomization to complete all the questionnaires.

Go/No-go decisions:

Safety: We are assuming that no more than 1 patients out of forty (2.5%) will have an adverse event of grade 4 or 5 that is at least possibly related to ENT-01 in this Stage. Should there be more than 1 patient with an AE grade 4 or 5 that is at least possibly related to Enterin-0 in this cohort

of 40 patients, the study will be put on an immediate safety hold until an emergency DSMB meeting can be held to evaluate the study for possible discontinuation.

Tolerability: We are assuming that all patients will exhibit a pro-kinetic effect at a dose lower than DLT and less than or equal to 175mg. Patients reaching DLT before a pro-kinetic effect will be terminated if the highest dose for the patient without a DLT was the STDE dose. Otherwise the patient will be treated at the highest dose at which they did not experience a DLT if they are randomized to the treatment arm (or will receive the equivalent dose of placebo).

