10 DATA MANAGEMENT AND STATISTICS

This is a trial with two stages. The Stage 1 portion will consist of 10 patients who will be dose escalated in single doses. Each patient will proceed through all the dose escalations starting at 25 mg and ending at 200 mg or at the dose at which s/he experiences a dose limiting toxicity (DLT). The doses to be tested are 25mg, 50mg, 75mg, 100mg, 125mg, 150mg, 175mg and 200mg. In the Stage 2 portion, all patients will go through a multiple dose escalation (3 dosing days at each dose) and the dose at which the patient experiences a consistent pro-kinetic effect (spontaneous, complete stool in at least 2/3 consecutive doses) without a DLT will be the dose for that patient. Patients who experience a DLT prior to reaching their pro-kinetic dose and at a dose equal to or less than the STDE dose will be terminated. Otherwise the patient will be assigned the highest dose at which they did not experience a DLT. If the patient reached 175 mg without a DLT and without a pro-kinetic dose, her/his dose will be 175 mg. The primary endpoint for the Stage 1 study is to determine whether the dose levels explored are safe and tolerable. The primary endpoint for the Stage 2 study is the regularization of bowel function as determined by stool frequency at the end of the fixed dose period compared to baseline. The Stage 2 portion will enroll 40 patients, with a target sample size of 34 evaluable patients. Six extra patients are enrolled to allow for patient withdrawals or terminations prior to the completion of the trial.

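### The Stage 1 automatic safety hold ignores related grade 4-5 events at 200 mg, the highest Stage 1 dose (low priority, one-phrase fix)

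*Protocol*

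**What the plan says.** In Stage 1, ten patients receive single doses rising in 25 mg steps from 25 to 200 mg. Section 3.1, Period 2.1 states: "This single dosing regimen will be continued until each patient has been given a single dose of 200mg", unless a dose-limiting event comes first. Section 10 agrees: "Each patient will proceed through all the dose escalations starting at 25 mg and ending at 200 mg".

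The Go/No-go paragraph of Period 2.1 first gives a planning assumption of at most one patient in ten, for events "of grade 4 or 5 that is at least possibly related to ENT-01 in dose levels thought to be below" (the sentence ends by naming the level at which the drug is expected to work). The action rule follows. With more than one patient having a grade 4 or 5 event at least possibly "related to ENT-01 for doses less than 200 mg, the study will be put on an immediate safety hold", pending an emergency DSMB meeting.

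The Stage 2 counterpart (Period 3.2, Go/No-go decisions) is set off by more "than 1 patient with an AE grade 4 or 5 that is at least possibly related to Enterin-0 in this cohort" of 40. It states no dose limit.

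Other oversight applies at 200 mg. Period 2.1 adds: "A review of safety, tolerability and adverse events will occur prior to administration of each dose level", and again with the DSMB at the end of Period 2. There are individual stopping criteria (Period 2.1), SAE reporting to the sponsor within 24 hours (sections 9.14 and 9.15), sponsor and investigator powers to stop (sections 4.5 and 12.11), and DSMB review and discretion (sections 9.20 and 9.21). Section 9.21 leaves stopping rules to a charter that is not among the documents.

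**The concern.** The hold is the only rule in these documents that forces a study-level pause when related life-threatening or fatal events recur in Stage 1. Its wording leaves out the dose at which exposure is highest. Followed literally, two such events at 200 mg, or one at 200 mg after one in another patient at a lower dose, would not set it off. Pausing would then be a matter of judgement.

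The people affected are those still waiting for 200 mg. Subjects 1-2 are scheduled for that dose one step before subjects 3-10, so up to eight patients could receive it after events in the first pair.

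**Working it through.** **The plan's own figures.** The Stage 1 assumption is 1/10 = 10% and the Stage 2 assumption is 1/40 = 2.5%. Both reproduce. The documents give no event rate for 200 mg, so every rate below is an assumption.

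**How the rule counts.** The hold needs at least two patients with a counted event. Each row refers to different patients.

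| Patients with event below 200 mg | Patients with event at 200 mg | Count as written | Hold? | Count at all doses | Hold? |
|---|---|---|---|---|---|
| 0 | 2 | 0 | no | 2 | yes |
| 1 | 1 | 1 | no | 2 | yes |
| 0 | 10 | 0 | no | 10 | yes |
| 2 | any | 2 | yes | 2 or more | yes |

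**Does the stated reason explain the cut?** The planning assumption concerns doses below therapeutic effect. Section 1.3 takes 100 mg as a possible prokinetic dose, the Stage 1 schematic uses 75 mg as its example of a dose that is tolerated by all and effective in some, and the Period 3.2 Tolerability paragraph assumes every patient responds at or below 175 mg. A cut placed at the edge of the therapeutic range would therefore fall well below 200 mg. The rule already covers doses expected to work and drops only the top one.

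**Timing.** In the Period 2.1 dosing table, 200 mg falls on D22-50 for subjects 1-2 and D25-57 for subjects 3-10. The early ends differ by 25 - 22 = 3 days and the late ends by 57 - 50 = 7 days, but the windows overlap from D25 to D50. Subjects 1-2 return for their next dose "after a minimum of a 72 hour observation period", and subjects 3-10 start only after the first pair has been observed for 72 hours at 25 mg. No minimum lead is stated at 200 mg itself.

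**What an all-dose hold would add before subjects 3-10 start 200 mg.** Let p be the chance of a related grade 4-5 event per patient at 200 mg. Assume independence, that subjects 1-2 both reach 200 mg, and that they do so ahead of the rest.

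- (a) No earlier event: both must have one, so the probability is p².
- (b) One of subjects 3-10 already had a counted event at a lower dose: at least one of subjects 1-2 must have one, so it is 1 - (1 - p)².

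| p | (a) | (b) |
|---|---|---|
| 0.01 | 0.0001 | 0.0199 |
| 0.05 | 0.0025 | 0.0975 |
| 0.10 | 0.01 | 0.19 |
| 0.20 | 0.04 | 0.36 |
| 0.30 | 0.09 | 0.51 |

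As written, 200 mg events contribute 0 in every cell.

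**Whether the hold fires at all in Stage 1.** If all ten are dosed at 200 mg and events occur only there, P(at least 2 of 10) = 1 - (1 - p)^10 - 10p(1 - p)^9 = 0.264, 0.624 and 0.851 at p = 0.10, 0.20 and 0.30, against 0 as written. If each patient also carries a 5% cumulative risk below 200 mg, the combined risk is 1 - 0.95(1 - p) = 0.145, 0.24 and 0.335. The hold then fires with probability 0.437, 0.733 and 0.898, against 0.086 as written. These larger figures overstate the practical gain, because many of those holds would come only after subjects 3-10 had begun taking 200 mg.

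**The case against.** The strongest reply is that 200 mg is not left unwatched. A safety review is required before each dose level, with no dose limit, and patients return for the next level only if there are no safety concerns. The sponsor would learn of a life-threatening event within 24 hours, and the DSMB may recommend a stop at any time. Two such events in subjects 1-2 could hardly pass unnoticed. This stands, and it is why the priority is low. It does not supply the missing trigger. The review has no stated numerical criterion, and the text does not say whether it is repeated between subjects 1-2 and subjects 3-10 at the same dose. Individual stopping at 200 mg ends a course already finished. The DSMB can only recommend. Its charter may cover 200 mg, but that cannot be checked here.

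Second, the cap may be deliberate, since the preceding sentence ties the rule to sub-therapeutic doses. It would be wrong to say that no reason is hinted at. The hint simply does not lead to 200 mg.

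Third, such events are expected to be rare. Section 1.3 predicts a peak plasma level of about 2 ng/ml at 200 mg and says that this dose "is covered by a safety margin of about 300x based on the rat, and about 70x based on the dog". That stands too, although the same section names local gastrointestinal effects as the principal uncertainty, and plasma levels say little about those.

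A reader might also infer that the Stage 1 and Stage 2 rules contradict each other, because only one has a cap. The documents do not support this. Under this protocol Stage 2 stops at 175 mg (sections 1.3, 3.1 and 10), so its unrestricted rule never reaches 200 mg. SAP section 2.1 reports a later amendment taking Stage 2 to 250 mg, but the amended protocol text is not in hand, and that change cannot show an inconsistency in the rules as written here.

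**Conclusion.** The point holds in a limited form. As written, the Stage 1 hold gives no weight to any number of related grade 4-5 events at 200 mg, and the stated rationale does not justify that cut.

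The exposure at stake is one single dose in up to eight patients. With no earlier event, the chance that an all-dose hold would act in time is 0.01 or less at assumed rates up to 10%. It reaches 0.19 to 0.51 only if another patient has already had a counted event and the rate is 10% to 30%. These figures rest on independence, on both first subjects reaching 200 mg, and on a lead over the others that the schedule implies but does not guarantee. With no lead, the gain before the others start is nil, although scheduling within the D25-57 window could spread subjects 3-10 and let a hold protect some of them.

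It should not be read as saying that patients at 200 mg lack safety oversight. The other safeguards would probably catch such events. What is absent is an automatic pause. This is worth considering because the correction is almost free.

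**What to change.** In the Period 2.1 Go/No-go paragraph of section 3.1, delete the phrase that restricts the count to doses under 200 mg, and delete the matching restriction to sub-therapeutic doses in the sentence before it. More than one patient with an at least possibly related grade 4 or 5 event at any Stage 1 dose, 25 to 200 mg, would then trigger the hold. Put the same wording in the DSMB charter.

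The cost is two phrases and a charter edit, with no extra patients or procedures. The downside is a slightly higher chance of a temporary pause late in Stage 1.
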